9.2 Agent Ordering

A drug supply request form is included in Appendix A.

10.1.2 Measurement of pre-metastatic niche density and pSTAT3

If patient consent is obtained, a total of 12 unstained slides derived from tumor and 12 unstained slides derived from normal lymph node tissue will be requested. Normal lymph node tissue will be assessed for pre-metastatic niche density, characterized as the number of clusters of VEGFR1⁺VLA-4⁺ cells per x 100 objective field.²⁹ This assessment will be performed through previously defined techniques.

pSTAT3 will be measured in paraffin-embedded sections. The authors of the protocol understand that collection procedures for specimens in this retrospective analysis are not standardized, and this may lead to inherent variability in pSTAT3 levels. Acknowledging this potential caveat, we would like to measure pSTAT3 and determine the relationship of this activated moiety to PFS. pSTAT3 will be determined through previously reported techniques.²⁴

11.0 Study Calendar

	Pre-Study	Wk 1	Wk 2	Wk 3	Wk 4	Wk 5	Wk 6	Wk 7	Wk 8	Wk 9	Wk 10	Wk 11	Wk 12 ^c	Off Study ^d
Pazopanib 800 mg oral daily ^a		X	X	X	X	X	X	X	X	X	X	X	X	
Informed consent	X													
Medical history	X													
Concurrent meds	X		X-----										X	
Physical exam	X	X		X		X			X					X
Vital signs	X	X		X		X			X					X
Height	X													
Weight	X	X		X		X			X					X
Performance Status	X	X		X		X			X					X
CBC w/diff, plts	X	X		X		X			X					X
Serum chemistry ^b	X	X		X		X			X					X
EKG	X													
Adverse event evaluation			X-----										X	
Tumor measurements	X													X ^d
Radiologic evaluation	X													X ^d
B-HCG (women of child-bearing potential)	X													
Collection of IL-6, E-selectin	X					X			X					X
UPC	X	X				X			X					X ^d
Collection of tumor specimens	X													

a: Excepting adjustments for toxicity. b: Albumin, alkaline phosphatase, total bilirubin, bicarbonate, BUN, calcium, chloride, creatinine, glucose, LDH, phosphorus, potassium, total protein, SGOT[AST], SGPT[ALT], sodium. c: After week 12, on study, continue daily oral pazopanib therapy as previous and repeat assessments noted at weeks 1, 3, 5 and 9 every 28 days. d: Off-study evaluation. Follow up will be every 6 months for survival.

12.0 Evaluation Criteria/Measurement of Effect

Response Criteria (Primary endpoint is confirmed response rate). To take place >28 days following a response. Otherwise events will be lost).

12.1

12.1.1 Evaluation of Target Lesions

Complete Response (CR): Disappearance of all target lesions

Partial Response (PR): At least a 30% decrease in the sum of the longest diameter (LD) of target lesions, taking as reference the baseline sum LD

Progressive Disease (PD): At least a 20% increase in the sum of the LD of target lesions, taking as reference the smallest sum LD recorded since the treatment started or the appearance of one or more new lesions

Stable Disease (SD): Neither sufficient shrinkage to qualify for PR nor sufficient increase to qualify for PD, taking as reference the smallest sum LD since the treatment started

12.1.2 Evaluation of Non-Target Lesions

Complete Response (CR): Disappearance of all non-target lesions and normalization of tumor marker level

Note: If tumor markers are initially above the upper normal limit, they must normalize for a patient to be considered in complete clinical response.

Stable Disease (SD): Persistence of one or more non-target lesion(s) and/or maintenance of tumor marker level above the normal limits

Progressive Disease (PD): Appearance of one or more new lesions and/or unequivocal progression of existing non-target lesions

Although a clear progression of “non-target” lesions only is exceptional, the opinion of the treating physician should prevail in such circumstances, and the progression status should be confirmed at a later time by the review panel (or Principal Investigator).

12.2 Best Response

12.2.1 The best overall response is the best response recorded from the start of the treatment until disease progression/recurrence (taking as reference for progressive disease the smallest measurements recorded since the treatment started).

Target Lesions	Non-Target Lesions	New Lesions	Overall Response	Best Response for this Category Also Requires:
CR	CR	No	CR	
CR	Non-CR/Non-PD	No	PR	
PR	Non-PD	No	PR	
SD	Non-PD	No	SD	documented at least once ≥ 4 wks. from baseline
PD	Any	Yes or No	PD	no prior SD, PR or CR
Any	PD*	Yes or No	PD	
Any	Any	Yes	PD	

* In exceptional circumstances, unequivocal progression in non-target lesions may be accepted as disease progression.

Note: Patients with a global deterioration of health status requiring discontinuation of treatment without objective evidence of disease progression at that time should be reported as "*symptomatic deterioration*". Every effort should be made to document the objective progression even after discontinuation of treatment.

13.0 Data Reporting/Protocol Deviations

13.1 Data Reporting

13.1.1 Confidentiality of Records

The original data collection forms will be stored at the originating institution in a secure location. When results of this study are reported in medical journals or at meetings, identification of those taking part will be withheld. Medical records of patients will be maintained in strictest confidence, according to current legal requirements. They will be made available for review, as required by the FDA or other authorized users such as the NCI, under the guidelines established by the Federal Privacy Act.

13.1.2 Patient Consent Form

At the time of registration, the original signed and dated patient's Informed Consent with the Experimental Subject's Bill of Rights (for the medical record). All Institutional, NCI, Federal, and State of California regulations concerning the Informed Consent form will be fulfilled. }

13.1.3 Data Collection Forms and Submission Schedule

All data will be collected in a timely manner protocol defined case report forms. Data will be sent to the City of Hope Department of Biostatistics and stored in a secure location.

13.1.3.1 *Eligibility Checklist*

The Eligibility Checklist must be completed by a protocol nurse or clinical research associate and signed by a participating investigator prior to registering the patient. See Section 4.3 for the registration procedure.

13.1.3.2 *Prior Therapy and On-Study Forms*

Within two weeks of registration, the clinical research associate will submit pre-study data collection forms.

13.2 Protocol Deviations

Protocol deviations must be submitted to the Data Coordinating Center. The clinical research associate at COH will also submit copies to the Protocol Management Team and the COH Data and Safety Management Board.

13.2.1 Deviation Policy

In accordance with the COH Policy on Clinical Research Protocol Deviation, there will be a "no deviations" rule for this protocol. However, for subject safety or unforeseen scheduling problems, planned deviations from this protocol will be permitted in accordance with COH IRB policies and if applicable, FDA approval.

13.2.2 Reporting of Unplanned Deviations

All unplanned deviations will be reported to the COH DSMB.

13.2.3 Resolving Disputes

If there is a dispute among the persons involved in the provision of research treatment, in regard to whether a treatment deviates from the protocol, the facts of the case will be reported to the DSMB which will be serve as the arbiter of whether a deviation exists.

14.0 Statistical Considerations

14.1 Study Design

The study is an open label, phase II assessment of pazopanib as 3rd-line therapy for mRCC.

14.1.1 Primary Endpoints

The primary endpoint is the confirmed response rate (CR+PR), as determined by the RECIST 1.1 criteria. We will employ the two stage MinMax design suggested by Simon.

Prior data indicates that an overall RR of 20% can be obtained with pazopanib therapy. For patients with mRCC eligible for this 3rd line study, a response rate of 20% would represent a significant improvement over current approaches (3rd line therapy with the Akt inhibitor perifosine, for instance, yielded a 7% response rate) and would further indicate that the activity of pazopanib is maintained through multiple prior lines of therapy in selected patients.

Prior studies suggest that a response rate between 5-10% would not be an improvement over current approaches. As a result, we have set a discouraging response rate at 8%, and an encouraging response rate at 23%. Initially, we will accrue 14 patients. If there is at least 1 responder, accrual will continue to 28 patients. If 5 or more responders (~18%) are observed, pazopanib will be declared promising for future studies, assuming toxicity and survival endpoints are also within acceptable limits. This Simon's MinMax two-stage design has a type I error of 10% (probability of declaring an agent with a true 8% response rate as promising), and a power of 80% (probability of *not* declaring an agent promising with a true 23% response rate is 20%). All eligible patients treated will be included in the calculation of response rate. Any patients with an unknown response rate will be included as a non-responder.

This design has 31% chance of stopping at the first stage if true response rate is 8%.

Toxicity will be monitored on an ongoing basis. If the number of unacceptable toxicities exceeds 1 in the first 3, or exceeds 2 in the first 6 or more than 25% thereafter, the study will hold accrual for an amendment regarding treatment modifications or study termination.

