Prior studies suggest that a response rate between 5-10% would not be an improvement over current approaches. As a result, we have set a discouraging response rate at 8%, and an encouraging response rate at 23%. Initially, we will accrue 14 patients. If there is at least 1 responder, accrual will continue to 28 patients. If 5 or more responders (18%) are observed, pazopanib will be declared promising for future studies, assuming toxicity and survival endpoints are also within acceptable limits. This Simon's MiniMax two-stage design has a type I error of 10% (probability of declaring an agent with a true 8% response rate as promising), and a power of 80% (probability of *not* declaring an agent promising with a true 23% response rate is 10%). All eligible patients treated will be included in the calculation of response rate. Any patients with an unknown response rate will be included as a non-responder.

This design has 31% chance of stopping at the first stage if true response rate is 8%.

Toxicity will be monitored on an ongoing basis. If the number of unacceptable toxicities exceeds 1 in the first 3, or exceeds 2 in the first 6 or more than 25% thereafter, the study will hold accrual for an amendment regarding treatment modifications or study termination. Toxicity will be graded and recorded for each patient in this population according to CTCAE 4.0.

Secondary endpoints include progression-free survival (PFS), overall survival (OS), and toxicity, and we will also compare PFS on this study to time to progression on the previous line of therapy.

Additional secondary endpoints relate to biological correlates, including E-Selection, IL-6, the pre-metastatic niche density, pSTAT3, and baseline HGF. Because the nature of these secondary endpoints is exploratory, we will not consider the issue of multiple comparisons and the according adjustment of p-values.

Univariate or multivariate Cox proportional hazards model will be invoked to assess the association of these biological correlates and both PFS and OS.

In addition, a t-test will be conducted to determine if there is an association between E-selectin, IL-6 and the pre-metastatic niche density.

Table of Contents

SECTION	PAGE
1.0 Goals and Objectives (Scientific Aims).....	17

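### The printed 10% type I error is the ceiling used to select the design; the response rule attains 6.75% at a true 8% rate, and the synopsis also misprints the type II error

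*Combined protocol and SAP*

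**What the plan says.** Section 14.1.1 (Primary Endpoints) sets out the whole primary decision.

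- Design: "We will employ the two stage MinMax design suggested by Simon".
- Rates: "we have set a discouraging response rate at 8%, and an encouraging response rate at 23"%.
- Stage 1: "Initially, we will accrue 14 patients". "If there is at least 1 responder, accrual will continue to 28 patients".
- Final rule: "If 5 or more responders (~18%) are observed, pazopanib will be declared promising for future studies". This is subject to toxicity and survival also being acceptable, and no numerical limits are attached to that condition in the paragraph.
- Error rate: the design "has a type I error of 10% (probability of declaring an agent with a true 8% response rate as promising"). The paragraph then gives 80% power at a true 23% rate, a 20% chance of missing that rate, and a 31% chance of stopping at stage 1 if the true rate is 8%.

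The synopsis (Statistical Considerations) carries the same text: "This Simon's MiniMax two-stage design has a type I error of 10"%, with the same definition at 8% and the same 80% power. There, however, the chance of not declaring the drug promising at a true 23% rate is printed as 10%.

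The 8% null is introduced with this reason: "Prior studies suggest that a response rate between 5-10% would not be an improvement over current approaches".

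**The concern.** The sentence does more than name a nominal level. Its parenthesis defines the type I error as the probability of a positive declaration at a true 8% rate, and the rule that determines this probability stands in the same paragraph. It can therefore be computed, and it is not 10%.

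This is the main error rate of a single-arm trial whose conclusion rests on 5 responders in 28. A reader who takes 10% at face value understates how strongly that result speaks against 8%. The neighbouring power and early-stopping figures are attained values, so the reader has no reason to treat this one differently.

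The synopsis adds a second problem. An 80% power and a 10% chance of missing the same alternative cannot both be true.

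**Working it through.** **Inputs**, all from Section 14.1.1: 14 patients in stage 1; continue with at least 1 responder; 28 in total, so 14 more in stage 2; success with at least 5 responders; null rate 8%, alternative 23%.

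**Formula.** With X1 the stage 1 responders and X2 the stage 2 responders, each binomial with 14 patients and rate p:

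P(success) = sum over x = 1 to 14 of P(X1 = x) × P(X2 ≥ 5 − x)

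P(early stop) = (1 − p)^14

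**Printed figures that reproduce**

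- Early stopping at 8%: 0.92^14 = 0.311. Printed 31%.
- Power at 23%: 0.8002. Printed 80%.
- Chance of missing a true 23% rate: 1 − 0.8002 = 0.1998. Section 14.1.1 prints 20%.

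**Printed figures that do not reproduce**

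Type I error at p = 0.08:

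| Stage 1 responders | P(X1 = x) | P(X2 ≥ 5 − x) | Product |
|---|---|---|---|
| 1 | 0.3788 | 0.0214 | 0.0081 |
| 2 | 0.2141 | 0.0958 | 0.0205 |
| 3 | 0.0745 | 0.3100 | 0.0231 |
| 4 | 0.0178 | 0.6888 | 0.0123 |
| 5 or more | 0.0035 | 1 | 0.0035 |
| Total | | | 0.0675 |

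The attained value is 6.75%, about a third below the printed 10%: (10 − 6.75)/10 = 32.5%.

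The synopsis figure of 10% for missing a true 23% rate also fails, because the design gives 20%.

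**Where the 10% comes from.** A search over all two-stage designs with type I error at most 10% at 8% and power at least 80% at 23% finds nothing smaller than 28 patients. Among the 28-patient designs, the plan's own (stop on 0 of 14; fail on 4 or fewer of 28) has the smallest expected size at 8%: 14 + 14 × (1 − 0.3112) = 23.6 patients. Ten percent is thus the search limit.

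**Could a slightly different rule give 10%?** None of those tried does, at a true 8% rate:

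- single stage, at least 5 of 28: 6.86%
- final cut-off of 4 instead of 5: 17.5%
- at least 2 responders required in stage 1: 5.94%

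**Could the synopsis 10% reflect a 90%-power design?** With the same 10% limit and 90% power, the minimax total would be 39 patients, not 28.

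**Probability of passing at other true rates under the plan's rule:** 1.15% at 5%, 10.0% at 9%, 14.0% at 10%.

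**The case against.** The best defence is that quoting the nominal level is common shorthand for a Simon design. The 10% limit is met with room to spare, the search under that limit gives exactly this design, and a reader misled at 8% is misled in the cautious direction. All of that stands, and it is why no change to the design follows. It does not rescue the sentence, which equates 10% with a defined probability that is 6.75%.

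A second objection also stands in part. The declaration further depends on acceptable toxicity and survival, so 6.75% is exact only for the response count. For the full declaration it is an upper bound. The added conditions can only lower it, and by an amount that cannot be computed without stated limits.

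A reader might go further and infer that the printed 10% is too low, because the plan regards rates of 5% to 10% as no improvement and the rule passes 14.0% of the time at a true 10% rate. The documents do not support that reading. They evaluate the type I error at 8% only and nowhere claim control across the range. Any point null placed inside a range gives a higher pass probability at the upper end. The 14.0% contradicts no printed figure; it bears on where the null was placed and is useful disclosure.

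**Conclusion.** The point holds as a misstatement of an operating characteristic, not as a design flaw. In both places the printed 10% is the selection ceiling, while the quantity that the text defines is 6.75% for the response rule. Separately, the synopsis figure of 10% for missing a true 23% rate is wrong and should be 20%.

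The calculation assumes independent responses, exactly 14 and then 28 patients in the denominators, and patients of unknown response counted as non-responders, as the plan provides. A reader might conclude that the trial is under-controlled or that its cut-offs need to move. Neither follows: the rule is conservative at the stated null, meets its power target, and is the minimax solution for the stated limits.

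**What to change.** In Section 14.1.1 and in the synopsis, replace the statement of a 10% type I error with wording such as: *type I error limited to 10% (attained 6.8% at a true 8% response rate, for the response-count rule alone; the toxicity and survival conditions can only lower it)*.

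In the same synopsis sentence, change the probability of not declaring the drug promising at a true 23% rate from 10% to 20%, to agree with 80% power and with Section 14.1.1.

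Optionally, as disclosure, add that the response rule passes with probability 10.0% at a true 9% rate and 14.0% at 10%, since the plan describes rates up to 10% as no improvement.

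The cost is one sentence in each of two places. The 28 patients, the stage 1 rule and the 5-responder threshold stay as they are.

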8.2 Monitoring and Personnel Responsible for Monitoring

The Protocol Management Team (PMT) consisting of the PI, collaborating investigator, CRA/protocol nurse, and statistician is responsible for monitoring the data and safety of this study, including implementation of the stopping rules for safety and efficacy.

Table 1: City of Hope PMT Reporting Timelines for the DSMC

Risk Level	Phase	Standard Reporting Requirement
RL 1, RL2, and Compassionate Use Studies	No reports required	
3	I	Every 3 months from activation date, as indicated in MIDAS
3	Pilot, Feasibility, II-IV	Every 6 months from activation date, as indicated in MIDAS

4	Pilot, Feasibility, I-IV	Every 3 months from activation date, as indicated in MIDAS
---	--------------------------------	--

Data and safety will be reported to the COH DSMC using the PMT report and submitted quarterly from the anniversary date of activation. Protocol specific data collection will include the following items: Adverse event reporting and quarterly safety assessment of pazopanib.

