14.1.2 Secondary Endpoints

Secondary endpoints include progression-free survival (PFS), overall survival (OS), and toxicity. Toxicity will use the CTCAE 4.0 and will summarize the worst grade per toxicity, per patient.

Additional secondary endpoints relate to biological correlates, including E-Selection, IL-6, the pre-metastatic niche density, pSTAT3, and baseline HGF. Because the nature of these secondary endpoints is exploratory, we will not consider the issue of multiple comparisons and the according adjustment of p-values.

To determine an association between E-selectin, IL-6 and pre-metastatic niche density, we will conduct a pairwise correlation test (linear regression). When the sample size is 28, the linear regression test of rho=0 (alpha = 0.050 one-sided) for one normally distributed covariate will have 80% power to detect a correlation coefficient of 0.435.

To determine if the biological correlates (e.g, IL-6, E-selectin, pSTAT3, and HGF), are associated with progression-free survival (PFS), we will fit univariate or multivariate Cox proportional hazards model and report the corresponding p-values. The same method will be employed to evaluate the prognostic effect of pre-metastatic niches.

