14.2 Sample Size Accrual Rate

The previously noted sample size of 28 patients is anticipated to accrue over the course of 12 months.

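### Does the toxicity hold rule contradict itself between patients 6 and 7 in a way that needs amending?

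*Combined protocol and SAP*

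**What the plan says.** The rule stands in section 14.1.1 and, with the same limits, in the statistical part of the synopsis: "If the number of unacceptable toxicities exceeds 1 in the first 3, or exceeds 2 in the first 6 or more than 25% thereafter". It has three parts: a count limit for the first three patients, a count limit for the first six, and a percentage limit after that. Crossing any of them holds accrual pending an amendment or termination. On timing the section says only that "Toxicity will be monitored on an ongoing basis". It gives no schedule of reviews and does not say whether the 25% covers all treated patients or only those after the sixth. It attaches no false-hold or detection probability to the rule.

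Section 8.2 makes the Protocol Management Team, which includes the statistician, "responsible for monitoring the data and safety of this study, including implementation of the stopping rules for safety and efficacy". Its reports to the data and safety monitoring committee are "submitted quarterly from the anniversary date of activation". Section 14.1.2 says that the toxicity analysis "will summarize the worst grade per toxicity, per patient", whereas the hold rule counts toxicities without saying whether the unit is the event or the patient.

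**The concern.** A monitoring limit should not become stricter in absolute count as patients are added. On the cumulative reading this one does, once. A team that accepted two events among six patients would have to stop accrual one patient later, even if the seventh patient had no event and the observed rate had fallen from 33.3% to 28.6%. One patient after that, the same two events would be acceptable again.

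At stake is an unnecessary or early interruption of a 28-patient, single-institution trial, and some embarrassment in applying a rule whose two limits disagree where they meet. The error is not towards a missed safety signal.

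**Working it through.** **Inputs.** The three limits come from section 14.1.1, and the maximum of 28 patients from sections 14.1.1 and 14.2. The documents state no true toxicity rate, so 5%, 10%, 20%, 25% and 30% are assumed. Also assumed: a cumulative 25%, at most one event per patient, independent patients, each outcome known before the next patient counts, and a review after every patient unless stated. The plan gives no probability for this rule, so there is no figure of its own to reproduce.

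**Step 1: the boundary.** The smallest count that forces a hold is 2 for n = 1 to 3, 3 for n = 4 to 6, and floor(n/4) + 1 from n = 7. For n = 1 to 28 this gives

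2, 2, 2, 3, 3, 3, **2**, 3, 3, 3, 3, 4, 4, 4, 4, 5, 5, 5, 5, 6, 6, 6, 6, 7, 7, 7, 7, 8.

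The only fall is at n = 7: 2/6 = 33.3% is tolerated, 2/7 = 28.6% is not, and 2/8 = 25.0% is.

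**Step 2: how often a trial meets the step.** Two events in six patients can be arranged in 15 ways. In 3 of these both events fall in the first three patients, and a hold has already occurred. That leaves 12 ways. With an event-free seventh patient,

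P(hold at 7, no new event) = 12 p²(1 − p)⁵.

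At p = 0.10 this is 12 × 0.01 × 0.59049 = 0.0709.

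**Step 3: how many of those holds are extra.** Many of these trials would hold later anyway if 2/7 were tolerated. The extra holds are the step 2 probability times P(no later hold by 28). At p = 0.10 this is 0.0709 × (1 − 0.3972) = 0.0427.

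| True rate | Hold at 7, no new event | Would hold later anyway | Extra holds (points) |
|---|---|---|---|
| 5% | 2.3% | 20.0% | 1.9 |
| 10% | 7.1% | 39.7% | 4.3 |
| 20% | 15.7% | 73.4% | 4.2 |
| 25% | 17.8% | 84.8% | 2.7 |
| 30% | 18.2% | 92.2% | 1.4 |

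**Step 4: chance of any hold by patient 28, by review schedule and by remedy.** Relaxed means that 2/7 is tolerated. Tightened means that two events force a hold at every review up to patient 7.

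| True rate | As written | Relaxed | Tightened | As written, reviews every 2 | As written, reviews every 3, and at 28 |
|---|---|---|---|---|---|
| 5% | 5.0% | 2.2% | 5.0% | 1.5% | 1.6% |
| 10% | 18.6% | 12.2% | 18.6% | 9.5% | 9.9% |
| 20% | 59.3% | 53.0% | 59.3% | 47.3% | 48.5% |
| 25% | 77.0% | 72.9% | 77.0% | 68.1% | 69.4% |
| 30% | 88.9% | 86.8% | 88.9% | 83.6% | 84.7% |

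Relaxing lowers the chance of a hold by 2.1 to 6.4 points. One third of that comes from trials at 1/6 whose seventh patient does have an event. Those are ordinary triggers, with 6 arrangements against the 12 above. Tightening leaves the overall chance unchanged but brings holds forward: P(hold by patient 6) rises from 3.6% to 11.4% at a true 10%, and from 32.1% to 58.0% at 30%.

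**Step 5: is a review at patient 7 likely?** Section 14.2 says: "The previously noted sample size of 28 patients is anticipated to accrue over the course of 12 months". Even accrual (an assumption) puts 28 × 3/12 = 7 patients on study at three months. That counts enrolments, not known outcomes. At one patient every 365/28 ≈ 13 days, the seventh has only just entered. If toxicity were judged over one 28-day cycle (the length is in section 6.1.1; its use as a window is an assumption), only 4 or 5 patients would have outcomes by then. The quarterly clock also runs from activation rather than first enrolment. The quarterly report therefore gives no particular reason to expect a review at exactly seven evaluable patients. Ongoing monitoring merely does not exclude one.

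**The case for a change.** The best case for amending is that the repair is short and the inconsistency exact. With a review after every patient, the allowance of two in six is empty. A trial at 2/6 must hold at patient 7 whatever happens, on 2/7 or on 3/7, which is why the tightened rule has the same overall hold probability. The other reading is no smoother. If the 25% covers only patients after the sixth, a single event in patient 7, 8 or 9 forces a hold (1/1, 1/2, 1/3). The unstated schedule also matters: at a true 10%, the chance of any hold is 18.6% with continuous review and 9.5% or 9.9% with sparser reviews.

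All of that is correct, but it does not identify a correction. One direction gives up 2.1 to 6.4 points of hold probability, and the other makes early holds more frequent. Choosing between them is a judgement about false holds against early detection, and nothing in the plan shows that its present balance is wrong. The gap between schedules is only partly due to the step. At 10%, removing it takes 18.6% to 12.2%, and the rest is the usual effect of looking more often.

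The missing denominator, review schedule, counting unit and definition of an unacceptable toxicity are real gaps in detail. They bear on every review, not only the seventh. The Protocol Management Team, with its statistician, can settle them when it sets up the monitoring.

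**Conclusion.** The step exists on the cumulative reading with reviews at both patient 6 and patient 7, but it does not call for a change. It is a coarse join between a count limit and a percentage limit in a small phase II rule. A team following the text literally would at worst hold accrual at 28.6%, which does exceed the stated 25%, after seeing one further outcome. An event-free seventh patient is new information even though it is not a new event.

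The extra chance of any hold is 1.4 to 4.3 points under the review schedule that exposes the step most fully, and at true rates of 25% to 30% the effect is mostly on timing. It is zero with reviews every two or every three patients. These sizes rest on the assumed rates, independent patients, one event per patient and immediately known outcomes. The primary response analysis and the conclusion drawn from it are unaffected.

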6.5 Criteria for Removal from Study

Treatment may continue until one of the following criteria applies:

- Disease progression,
- Intercurrent illness that prevents further administration of treatment,
- Unacceptable adverse event(s),
- Patient decides to withdraw from the study,
- General or specific changes in the patient's condition render the patient unacceptable for further treatment in the judgment of the investigator, or
- Treatment delays of > 2 weeks due to adverse events.

Treatment may be interrupted within a cycle for up to 2 weeks and missed doses should be omitted. However, patients will be replaced if they do not receive at least 80% of the planned treatment in the first cycle of therapy.

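### The toxicity hold rule drops for one patient: 2 affected of 6 is allowed, 2 of 7 requires a hold even if patient 7 is unaffected, and 2 of 8 would be allowed

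*Combined protocol and SAP*

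**What the plan says.** The rule stands in section 14.1.1 and, in the same words, in the statistical part of the synopsis. Accrual is held "If the number of unacceptable toxicities exceeds 1 in the first 3, or exceeds 2 in the first 6 or more than 25% thereafter". It is not tied to scheduled looks: "Toxicity will be monitored on an ongoing basis". If a limit is crossed, "the study will hold accrual for an amendment regarding treatment modifications or study termination". Section 8.2 makes the Protocol Management Team, which includes the statistician, responsible for monitoring, "including implementation of the stopping rules for safety and efficacy". On timing, section 14.2 says: "The previously noted sample size of 28 patients is anticipated to accrue over the course of 12 months".

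The plan does not say whether events or patients are counted, whether the percentage clause is cumulative, or how likely a hold is under any true toxicity rate.

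**The concern.** The rule joins two count limits to a percentage limit. With ongoing monitoring it has to be read at patient 7, where the percentage clause starts. Two affected patients among the first 6 are acceptable. If patient 7 then tolerates the drug, the evidence has become more reassuring, yet the rule now requires a hold. With 8 patients treated, the same two affected patients would be acceptable.

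Moving from a 33% allowance to 25% is a reasonable aim, but a limit that falls for one patient and then rises again does not do that.

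This is the only trial-level numerical toxicity limit I find in the plan, and its wording is mandatory. Section 13.2.1 allows planned deviations for subject safety or scheduling, which does not describe carrying on past a safety limit. The team would therefore either pause a 28-patient single-site trial halfway through its 14-patient first stage, or override its own rule.

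**Working it through.** **Inputs.** From 14.1.1: hold at more than 1 in the first 3, more than 2 in the first 6, more than 25% after that; continuous monitoring. From 14.2: 28 patients in 12 months. Assumed: the count is patients with at least one unacceptable toxicity, cumulative over patients treated; each patient is affected independently with probability p; p is varied because the documents give no rate. The plan states no hold probability, so there is no figure of its own to reproduce.

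**Step 1: the limits.** Let T(n) be the number of affected patients that triggers a hold with n treated. T = 2 for n = 1 to 3 and T = 3 for n = 4 to 6. For n ≥ 7, T is the smallest k with k/n > 0.25.

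- n = 6: 2/6 = 33.3%, allowed; T = 3.
- n = 7: 1/7 = 14.3%, allowed; 2/7 = 28.6%, hold; T = 2.
- n = 8: 2/8 = 25.0%, not above 25%, allowed; T = 3.

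After that T is 3 for n = 8 to 11, 4 for 12 to 15, 5 for 16 to 19, 6 for 20 to 23, 7 for 24 to 27, and 8 at 28. T falls only at n = 7.

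**Step 2: hold at patient 7 with patient 7 unaffected.** This needs exactly 2 of the first 6 affected, not both among the first 3 (that would already have caused a hold), then an unaffected patient 7:

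[C(6,2) − C(3,2)] p²(1−p)⁵ = (15 − 3) p²(1−p)⁵ = 12 p²(1−p)⁵

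- p = 0.10: 12 × 0.01 × 0.59049 = 0.0709
- p = 0.20: 12 × 0.04 × 0.32768 = 0.1573

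**Step 3: any hold by patient 28.** Let a(n,k) be the probability of k affected among n with no hold so far. Then a(n,k) = (1−p) a(n−1,k) + p a(n−1,k−1) for k < T(n), and 0 otherwise. The hold probability is 1 − Σ a(28,k). The changed rule differs only in T(7) = 3.

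| True rate (assumed) | As written | T(7) = 3 | Difference |
|---|---|---|---|
| 10% | 18.6% | 12.2% | 6.4 points |
| 20% | 59.3% | 53.0% | 6.3 points |
| 30% | 88.9% | 86.8% | 2.1 points |
| 40% | 98.5% | 98.2% | 0.3 points |

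**Step 4: where the difference comes from.** Only paths at exactly 2 of 7 are treated differently. They arise from 2 of 6 with patient 7 unaffected, 12p²(1−p)⁵, or from 1 of 6 with patient 7 affected, 6p × (1−p)⁵ × p = 6p²(1−p)⁵. The chance that such a path meets no later limit is 0.6028 at 10% and 0.2656 at 20%.

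- 10%: 0.0709 × 0.6028 = 4.3 points (unaffected) and 0.0354 × 0.6028 = 2.1 points (affected); total 6.4.
- 20%: 0.1573 × 0.2656 = 4.2 points and 0.0786 × 0.2656 = 2.1 points; total 6.3.

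**Step 5: delayed onset.** Steps 2 to 4 assume that each outcome is known before the next patient is counted. A simulation entered one patient every 365/28 = 13.0 days, with onset uniform over W days and all treated patients in the denominator. The ranges cover two ways of applying the early clauses: to the number treated at the time, or to those named first patients.

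| W | Difference at 10% | Difference at 20% |
|---|---|---|
| 28 days | 5.5–5.9 points | 5.7–6.1 points |
| 56 days | 3.7–4.8 points | 4.4–5.6 points |
| 84 days | 2.3–3.4 points | 2.8–4.4 points |

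**The case against.** **The error is cautious.** 2 of 7 is above the plan's own 25% ceiling, and the consequence is a pause for an amendment or a termination decision. This stands, and it keeps the point minor. A reader might infer that the rule under-protects patients or ends the trial automatically; the text supports neither.

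**Many of these holds would come anyway.** At a 20% rate, 73% of the holds with patient 7 unaffected would have met a later limit (1 − 0.2656). At 10% it is 40% (1 − 0.6028), so there most of them are holds that nothing else in the rule would have caused.

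**A reader might credit the whole 6.4 points to a seventh patient who tolerated the drug.** About a third, 2.1 points, comes from 1 of 6 followed by an affected patient 7, where the hold follows a new toxicity.

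**The percentage clause might count only patients after the sixth.** The text allows this reading, though the cumulative one is more natural. It avoids the anomaly, since an unaffected patient 7 gives 0/1. It has a separate small-denominator problem: one affected patient at position 7, 8 or 9 gives up to 1/1, 1/2 or 1/3, all above 25%.

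**Patient 8 may never be counted.** A hold at 7 stops accrual, so 2 of 8 arises only if patient 8 is already enrolled or accrual resumes. This is correct about the sequence of events. It does not change the limits.

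**Other oversight exists.** Section 8.2 provides quarterly reports to the data and safety monitoring committee. That limits the harm but does not change what the rule requires at patient 7.

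**Conclusion.** The point holds as a minor correction. On the cumulative patient count, the limit falls at patient 7 and recovers at patient 8, and nothing elsewhere in the plan repairs it. If outcomes are known promptly, the dip adds 6.4 points to the chance of a hold at an assumed 10% rate and 6.3 points at 20%; about two thirds of that comes from an unaffected patient 7. Across the delayed-onset settings examined, the addition is 2.3 to 6.1 points.

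The arithmetic of the limits depends only on the wording and the counting basis. The probabilities also depend on assumed toxicity rates, independence between patients and onset times, none of which the documents give. The primary response analysis is not affected.

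**What to change.** In 14.1.1 and the synopsis, apply the limit of 2 to the first 7 patients instead of the first 6, with the 25% clause starting after that. Equivalently, give a table counted in patients with at least one unacceptable toxicity:

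| Patients treated | Hold when affected patients reach |
|---|---|
| 1–3 | 2 |
| 4–11 | 3 |
| 12–15 | 4 |
| 16–19 | 5 |
| 20–23 | 6 |
| 24–27 | 7 |
| 28 | 8 |

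These equal the written limits everywhere except at patient 7. The table is preferable because it also settles the unit of counting and the cumulative reading.

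The same amendment could usefully say which grades and attributions count as unacceptable, which the plan leaves open. It could also say whether patients replaced under section 6.5 ("patients will be replaced if they do not receive at least 80% of the planned treatment in the first cycle of therapy") stay in the count; I would keep them. These are separate gaps in detail.

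The cost is a wording amendment in two places, with no new visits, data or committee. The downside is slightly fewer holds when toxicity is truly high: 88.9% to 86.8% at a 30% rate and 98.5% to 98.2% at 40%.
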